10.6.1 Protocol Amendment(s)/Administrative Change(s)

Amendment 1 Approval Date: 31 Mar 2020

PURPOSE:

To review the trial design schematic because it was targeting only subjects on antidepressants. To review the safety endpoints at and after the end of IMP administration. To clarify the procedures at discontinuation of IMP administration. To review the stipulations for restricted medications. To change the descriptions due to a change in the total volume of blood to be collected in the laboratory tests and a review on the safety endpoints after the finalization of the protocol version 1. To change the calculation method for confidential intervals. To review the stipulations for prohibited medications in consideration of subject safety.

BACKGROUND:

The trial design schematic was amended so that it can be applied to all subjects regardless of the use of antidepressants. The safety endpoints at and after the end of IMP administration were reviewed and amended. The procedures at discontinuation of IMP administration were amended for clarification. The stipulations for restricted medications were amended for clarification. The descriptions were changed based on the change to the total volume of blood to be collected in the laboratory tests and the review of the safety endpoints after the finalization of the protocol version 1. The calculation method for confidence intervals was amended to a method corresponding to differences between the groups. The stipulations for prohibited medications were amended in consideration of subject safety.

MODIFICATIONS TO PROTOCOL:

Location	Before amendment	After amendment
Figure 1.2-1	-	Replacement
Table 1.3-1	-	Visit 10: Addition of vital signs
		Visit 11: Deletion of the laboratory tests
		and vital signs
		Addition of annotations j, k, and l
1.4.6 Visit 11	The investigator will perform Visit 11	The investigator will perform Visit 11
	observations and examinations 14 days	observations and examinations 14 days
	$(\pm 7 \text{ days})$ after the date of last IMP dose	(\pm 7 days) after the date of last IMP dose
	in all subjects who have completed or	in all subjects who started IMP
	discontinued IMP treatment. The	administration after Visit 3. The
	investigator will register the required	investigator will register the required
	information in the IRT system at the end	information in the IRT system at the end
	of the post-treatment observation period	of the post-treatment observation period
1 4 7 44	for each subject.	for each subject.
1.4.7 At Discontinuation	If trial discontinuation occurs during the	If discontinuation of IMP administration
Discontinuation	double-blind treatment period or double-	occurs during the period between the start of IMP administration after Visit 2
	blind tapering period, the investigator will perform the examination at	and the start of IMP administration after
	discontinuation specified in the schedule	Visit 9, the investigator will perform the
	of assessments, and record the results and	examination at discontinuation specified
	visit date in the source document and	in the schedule of assessments, and
	eCRF. The investigator will register the	record the results and the visit date in the
	required information in the IRT system.	source document and eCRF. The
	If discontinuation occurs during the	investigator will register the required
	period between the start of IMP	information in the IRT system.
	administration after Visit 4 and the start	If discontinuation occurs during the
	of IMP administration after Visit 9, the	period between the start of IMP
	IMP dose will be tapered (duration: 1	administration after Visit 2 and the start
	week [7 days \pm 2 days]), and then the	of IMP administration after Visit 3, it is
	subject will visit the trial site to undergo	not necessary to perform the post-
	the same examination as scheduled at	treatment observation (Visit 11) 2 weeks
	Visit 10, and the post-treatment	after the date of the final dosing after the
	observation (Visit 11) will be performed	examination at discontinuation has been
	2 weeks after the date of the final dosing. However, if the investigator judges that	performed. If discontinuation account during the
	the IMP needs to be discontinued due to	If discontinuation occurs during the period between the start of IMP
	an adverse event (AE) or if the IMP dose	administration after Visit 4 and the start
	cannot be tapered due to the subject's	of IMP administration after Visit 9, the
	circumstances such as he/she does not	IMP dose will be tapered (duration: 1
	wish to taper the dose, dose tapering is	week [7 days \pm 2 days]) after the
	not mandatory. If discontinuation occurs	examination at discontinuation has been
	during the period between the start of	performed, and then the subject will visit
	IMP administration after Visit 3 and the	the trial site to undergo the same
	start of IMP administration after Visit 4	examination as scheduled at Visit 10, and
	or between the start of IMP	the post-treatment observation (Visit 11)
	administration after Visit 9 and Visit 10,	will be performed 2 weeks after the date
	dose tapering is not necessary, and the	of the final dosing. However, if the
	post-treatment observation (Visit 11) will	investigator judges that the IMP needs to
	be performed 2 weeks after the date of	be discontinued due to an adverse event
	the final dosing.	(AE) or if the IMP dose cannot be
		tapered due to the subject's
		circumstances such as he/she does not
		wish to taper the dose, dose tapering is

		not mandatory, and the examination required at discontinuation will be performed followed by the post-treatment observation (Visit 11) 2 weeks after the date of the final dosing. If discontinuation occurs during the period between the start of IMP administration after Visit 3 and the start of IMP administration after Visit 4, dose
		tapering is not necessary after the examination at discontinuation has been performed, and the post-treatment observation (Visit 11) will be performed 2 weeks after the date of the final dosing. If discontinuation of IMP administration occurs during the period between the start of IMP administration after Visit 9 and Visit 10, the examination at discontinuation is not necessary, the subject will visit the trial site to undergo
		the same examination as scheduled at Visit 10, and the post-treatment observation (Visit 11) will be performed 2 weeks after the date of the final dosing.
6.5.1 Prohibited Medications 6.5.1.2 Visit 2 Through Visit 9	 Antidepressants Benzodiazepines (except for ultrashortacting hypnotics and sedatives) Drugs that are considered to affect the metabolic/activity systems of serotonin, noradrenaline, or dopamine Strong cytochrome P450 (CYP) 3A4 inhibitors, CYP1A2 inhibitors, CYP2D6 inhibitors, CYP3A4 inducers, CYP1A2 inducers, CYP2B6 inducers, and CYP2D6 substrate with narrow therapeutic range (except for topical drugs) Central nervous system drugs (except for ultrashort-acting hypnotics and sedatives; antipyretic, analgesic and anti-inflammatory agents; and general cold medicines) Chinese herbal medicines (drugs indicated for neurosis, anxiety neurosis, neurasthenia, and insomnia) Over the counter drugs used as sleeping pills Supplements used for improvement of depressive symptoms (St. John's wort, S-adenosylmethionine [SAM-e], ω-3 fatty acid, kava extract, γ-aminobutyric acid [GABA]) Varenicline 	 2 weeks after the date of the final dosing. 6.5.1.2 Visit 2 Through Visit 9 Antidepressants Benzodiazepines (except for ultrashortacting hypnotics and sedatives) Drugs that are considered to affect the metabolic/activity systems of serotonin, noradrenaline, or dopamine Central nervous system drugs (except for ultrashort-acting hypnotics and sedatives; antipyretic, analgesic and antiinflammatory agents; and general cold medicines) Chinese herbal medicines (drugs indicated for neurosis, anxiety neurosis, neurasthenia, and insomnia) Over the counter drugs used as sleeping pills Supplements used for improvement of depressive symptoms (St. John's wort, Sadenosylmethionine [SAM-e], ω-3 fatty acid, kava extract, γ-aminobutyric acid [GABA]) Varenicline 6.5.1.3 Visit 2 Through Visit 10 Strong cytochrome P450 (CYP) 3A4 inhibitors, CYP1A2 inhibitors, CYP2D6 inhibitors, CYP2B6 inducers, and CYP2D6 substrate with narrow therapeutic range (except for topical drugs)

6.5.2 Restricted Medications 6.5.2.1 Visit 2 Through Visit 9

• Antipyretic, analgesic and antiinflammatory agents, and antihistamines The concomitant use of these drugs is permitted if they have been used for treatment of a complication at Visit 2. However, the same dosage and administration should be maintained unless an AE has occurred, or the drug is judged to be no longer necessary due to remission of symptoms. Short-term concomitant use of these drugs for treatment of colds is also permitted. The use of local topical drugs is permitted.

· Antipyretic, analgesic and antiinflammatory agents, and antihistamines The concomitant use of these drugs is permitted if they have been used for treatment of a complication at Visit 2. However, the same dosage and administration should be maintained unless an AE has occurred, or the drug is judged to be no longer necessary due to remission of symptoms. Short-term concomitant use of these drugs for treatment of colds is also permitted. The use of local topical drugs is permitted. Short-term is defined as 1 week in principle. If antipyretic, analgesic and anti-inflammatory agents or antihistamines that were not being used at informed consent are administered for > 2 weeks, or such administration is necessary, the trial will be discontinued according to the reason for discontinuation, "significant protocol deviation."

7.3.2 Treatment Discontinuation

<Paragraph 2 and onward>
If discontinuation of IMP administration occurs, the examination at discontinuation will be performed. If the subject refuses to undergo any examinations at the time of withdrawal, or if examinations cannot be performed due to an emergency or other circumstances, of the examination items specified for the time of withdrawal, only those items that can be performed will be performed.

If discontinuation is decided during the period between the start of IMP administration after Visit 4 and the start of IMP administration after Visit 9, the IMP dose will be tapered (duration: 1 week [7 days \pm 2 days]) wherever possible (see Section 6.1.1.4). After dose tapering, the subject will visit the trial site to undergo the same examination as scheduled at Visit 10, and the posttreatment observation (Visit 11) will be performed 2 weeks after the date of the final dosing. If discontinuation occurs during the period between the start of IMP administration after Visit 3 and the start of IMP administration after Visit 4 or between the start of IMP administration after Visit 9 and Visit 10, dose tapering is not necessary, and the post-treatment observation (Visit 11) will be performed 2 weeks after the date of

<Paragraph 2 and onward>
If discontinuation of IMP administration occurs during the period between the start of IMP administration after Visit 2 and the start of IMP administration after Visit 9, the examination at discontinuation will be performed. If the subject refuses to undergo any examinations at the time of withdrawal, or if examinations cannot be performed due to an emergency or other circumstances, of the examination items specified for the time of withdrawal, only those items that can be performed will be performed.

If discontinuation occurs during the period between the start of IMP administration after Visit 2 and the start of IMP administration after Visit 3, the post-treatment observation (Visit 11) 2 weeks after the final dosing is not necessary after the examination at discontinuation has been performed. If discontinuation is decided during the period between the start of IMP administration after Visit 4 and the start of IMP administration after Visit 9, the IMP dose will be tapered (duration: 1 week [7 days \pm 2 days]) wherever possible after the examination at discontinuation has been performed (see 6.1.1.4). After dose tapering, the subject will visit the trial site to undergo the

	the final dosing.	same examination as scheduled at Visit
		10, and the post-treatment observation
		(Visit 11) will be performed 2 weeks
		after the date of the final dosing.
		If discontinuation occurs during the period between the start of IMP
		administration after Visit 3 and the start
		of IMP administration after Visit 4, dose tapering is not necessary after the
		examination at discontinuation has been
		performed, and the post-treatment
		observation (Visit 11) will be performed
		2 weeks after the date of the final dosing.
		If discontinuation of IMP administration
		occurs during the period between the
		start of IMP administration after Visit 9
		and Visit 10, the examination at
		discontinuation is not necessary. The
		subject will visit the trial site to undergo
		the same examination as scheduled at
		Visit 10 , and the post-treatment
		observation (Visit 11) will be performed
		2 weeks after the date of the final dosing.
8.7.1 Clinically	The total volume of blood to be collected	The total volume of blood to be collected
Laboratory	is 68 mL.	is approximately 38 mL.
	 MADRS response rate 	 MADRS response rate
	 MADRS remission rate 	MADRS remission rate
	CGI-I improvement rate	CGI-I improvement rate
-	The MADRS response rate in the OPC-	The MADRS response rate in the OPC-
Analysis	64005 20-mg group will be compared	
	with that in the placebo group using the	with that in the placebo group using the
	γ^2 test in the LOCF dataset. The	γ^2 test in the LOCF dataset. The
	· · ·	
	 	-
	will be determined. The MADRS	determined. The MADRS remission rate
	remission rate and CGI-I improvement	and CGI-I improvement rate will be
	rate will be analyzed in the same manner	analyzed in the same manner as the
	as the MADRS response rate.	MADRS response rate.
Laboratory Assessments 9.4.1.3 Secondary Efficacy Endpoint Analysis	 MADRS response rate MADRS remission rate CGI-I improvement rate The MADRS response rate in the OPC-64005 20-mg group will be compared with that in the placebo group using the χ² test in the LOCF dataset. The differences in the response rates between each OPC-64005 group and the placebo group, as well as the two-sided 95% CI (Clopper-Pearson confidence interval), will be determined. The MADRS remission rate and CGI-I improvement rate will be analyzed in the same manner 	• MADRS remission rate • CGI-I improvement rate The MADRS response rate in the OPC-64005 20-mg group will be compared with that in the placebo group using the χ^2 test in the LOCF dataset. The differences in the response rates between each OPC-64005 group and the placebo group, as well as the two-sided 95% CI (Wald confidence interval), will be determined. The MADRS remission rate and CGI-I improvement rate will be analyzed in the same manner as the

ADDITIONAL RISK TO THE SUBJECT:

There is no additional risk to the subjects.

This statistical analysis plan documents the details of the statistical analysis methodology to be applied in the protocol of Trial 277-102-00027.

2 Trial Objectives

The objective of the trial is to compare the efficacy of OPC-64005 at 20 mg vs placebo and to assess the safety and pharmacokinetics (PK) of OPC-64005 at 10 and 20 mg in patients with major depressive disorder (MDD).

3 Trial Design

3.1 Type/Design of Trial

In this trial, OPC-64005 at 10 mg or 20 mg or placebo will be orally administered as repeated doses once daily for 6 weeks in 270 patients with MDD, and the efficacy, safety, and PK of OPC-64005 will be assessed. This is a phase 2, multi-center, randomized, double-blind, placebo-controlled, parallel-group comparison trial consisting of 5 periods: screening period, placebo lead-in period (single-blind with subjects blinded to treatment received), double-blind treatment period, double-blind tapering period, and post-treatment observation period.

[figure not shown]

Figure 3.1-1 Trial Design Schematic

3.2 Trial Treatments

3.2.1 Placebo Lead-in Period (Single-blind With Subjects Blinded to Treatment Received)

Two placebo tablets will be administered orally once daily for 1 week.

3.2.2 Double-blind Treatment Period

- Placebo group

Two placebo tablets will be administered orally once daily for 6 weeks.

- OPC-64005 10-mg group

One placebo tablet and one OPC-64005 10-mg tablet will be administered orally once daily for 6 weeks.

- OPC-64005 20-mg group

One placebo tablet and one OPC-64005 10-mg tablet will be administered orally once daily for 1 week, followed by two OPC-64005 10-mg tablets for 5 weeks.

3.2.3 Double-blind Tapering Period

- Placebo group

Two placebo tablets will be administered orally once daily for 1 week.

- OPC-64005 10-mg group

Two placebo tablets will be administered orally once daily for 1 week.

- OPC-64005 20-mg group

One placebo tablet and one OPC-64005 10-mg tablet will be administered orally once daily for 1 week.

3.2.4 At Discontinuation

If discontinuation occurs during the period between the start of IMP administration after Visit 4 and the start of IMP administration after Visit 9, the IMP dose will be tapered (1 week [7 days \pm 2 days]) to the following regimens (however, if the investigator judges that the IMP needs to be discontinued due to an adverse event (AE) or if the IMP dose cannot be tapered due to the subject's circumstances such as he/she does not wish to taper the dose, dose tapering is not mandatory):

- Placebo group

Two placebo tablets will be administered orally once daily for 1 week.

- OPC-64005 10-mg group

Two placebo tablets will be administered orally once daily for 1 week.

- OPC-64005 20-mg group

One placebo tablet and one OPC-64005 10-mg tablet will be administered orally once daily for 1 week.

If discontinuation occurs during the period between the start of IMP administration after Visit 3 and the start of IMP administration after Visit 4 or between the start of IMP administration after Visit 9 and Visit 10, dose tapering is not necessary. If the IMP dose is tapered after discontinuation, the IMP will be dispensed according to the instructions from the IRT system, as the IMP will be administered under double-blind conditions.

3.3 Trial Population

The trial population is 270 male and female patients ≥ 20 to < 65 years of age (at time of informed consent) diagnosed with either “major depressive disorder, single episode” or “major depressive disorder, recurrent episode” according to the Diagnostic and Statistical Manual of Mental Disorders, Fifth Edition (DSM-5).

3.4 Trial Visit Window

For all endpoints, acceptable windows for analysis are specified, and analysis should take place at the analysis time points regardless of the time points recorded on the case report form.

Acceptable windows for analysis in the double-blind treatment period are shown in Table 3.4-1. Day 1 is defined as the start day of IMP administration in the double-blind treatment period. If multiple data exist within an acceptable window, the last data within the window will be used in analysis. Data obtained 7 days or later after the final IMP administration in the double-blind treatment period will be excluded from analysis performed at any time point in the double-blind treatment period. Data obtained on the day after the start of IMP administration in the double-blind tapering period and thereafter will also be excluded from analysis performed at any time point in the double-blind treatment period.

Table 3.4-1 Acceptable Windows for Analysis in the Double-blind Treatment Period		
Week	Target Day	Trial Day Interval
Baseline	1	After the start of IMP administration in the placebo lead-in period to 1
Week 1 in the double-blind treatment period	8	2-11
Week 2 in the double-blind treatment period	15	12-18
Week 3 in the double-blind treatment period	22	19-25
Week 4 in the double-blind treatment period	29	26-32
Week 5 in the double-blind treatment period	36	33-39
Week 6 in the double-blind treatment period	43	40-50

Time points recorded on the case report form will be used in analysis in the double-blind tapering period (Week 7) and the post-treatment observation period.

3.5 Handling of Endpoints

3.5.1 Montgomery Åsberg Depression Rating Scale

The Montgomery-Åsberg Depression Rating Scale (MADRS) total score will be the total score of MADRS Items 1 through 10. The MADRS anhedonia factor score will be the total score of MADRS Items 1, 2, 6, 7, and 8.

3.5.2 Clinical Global Impression - Improvement

“0. Not assessed” will be handled as missing data.

3.5.3 Clinical Global Impression - Severity of Illness

“0. Not assessed” will be handled as missing data.

3.5.4 Hamilton Rating Scale for Depression

The Hamilton Rating Scale for Depression (HAM-D) 17-item total score will be the total score of HAM-D Items 1 through 17.

3.5.5 Montgomery Åsberg Depression Rating Scale Self-assessment

The Montgomery Åsberg Depression Rating Scale Self-assessment (MADRS-S) total score will be the total score of MADRS-S Items 1 through 9.

3.5.6 Apathy Scale

The Apathy Scale score will be the total score of Apathy Scale Items 1 through 14.

4 Sample Size

As no clinical trials of OPC-64005 in patients with MDD have been previously conducted, the target number of subjects was determined based on the results from another antidepressant clinical trial using MADRS score as the primary endpoint. In the phase 3 clinical trial of escitalopram conducted outside Japan, the mean change (\pm SE) from baseline in MADRS total score at the final time point of Week 8 (8 weeks after start of administration) determined using last observation carried forward analysis of covariance was -9.4 ± 0.9 in the placebo group ($n = 119$), -12.0 ± 0.9 in the citalopram 40-mg group ($n = 125$), -12.8 ± 0.8 in the escitalopram 10-mg group ($n = 118$), and -13.9 ± 0.8 in the escitalopram 20-mg group ($n = 123$). Referring to those results, in the present trial it is assumed that the difference between the OPC-64005 20-mg group and the placebo group in the change from baseline in MADRS total score at Week 6 of the double-blind treatment period will be -4 with a standard deviation of 11. To ensure a power of 80% in a two-sided test with a significance level of 0.05, 120 subjects each are

required for the OPC-64005 20-mg group and the placebo group. For the OPC-64005 10-mg group, the number of subjects was set at 30 without statistical consideration. The planned number of subjects to be randomized for the trial was therefore set at 270.

5 Statistical Analysis Datasets

5.1 Full Analysis Set

The full analysis set (FAS) includes all subjects who were administered at least 1 dose of double-blind IMP and have MADRS total scores at baseline and at least one time point after the start of double-blind treatment.

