1.4.7 At Discontinuation

If discontinuation of IMP administration occurs during the period between the start of IMP administration after Visit 2 and the start of IMP administration after Visit 9, the investigator will perform the examination at discontinuation specified in the schedule of assessments, and record the results and the visit date in the source document and eCRF. The investigator will register the required information in the IRT system.

If discontinuation occurs during the period between the start of IMP administration after Visit 2 and the start of IMP administration after Visit 3, it is not necessary to perform the post-treatment observation (Visit 11) after the examination at discontinuation has been performed.

If discontinuation occurs during the period between the start of IMP administration after Visit 4 and the start of IMP administration after Visit 9, the IMP dose will be tapered (duration: 1 week [7 days \pm 2 days]) after the examination at discontinuation has been performed, and then the subject will visit the trial site to undergo the same examination as scheduled at Visit 10, and the post-treatment observation (Visit 11) will be performed 2 weeks after the date of the final dosing. However, if the investigator judges that the IMP needs to be discontinued due to an adverse event (AE) or if the IMP dose cannot be tapered due to the subject's circumstances such as he/she does not wish to taper the dose, dose tapering is not mandatory, and the examination at discontinuation will be performed followed by the post-treatment observation (Visit 11) 2 weeks after the date of the final dosing.

If discontinuation occurs during the period between the start of IMP administration after Visit 3 and the start of IMP administration after Visit 4, dose tapering is not necessary after the examination at discontinuation has been performed, and the post-treatment observation (Visit 11) will be performed 2 weeks after the date of the final dosing.

If discontinuation of IMP administration occurs during the period between the start of IMP administration after Visit 9 and Visit 10, the examination at discontinuation is not necessary, the subject will visit the trial site to undergo the same examination as scheduled at Visit 10, and the post-treatment observation (Visit 11) will be performed 2 weeks after the date of the final dosing.

2 Introduction

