In Trial 277-201-00001, on the other hand, the incidence of AEs that led to discontinuation of the trial in the OPC-64005 group was 23.4% (18/77 subjects) and higher than that in the placebo group (8.5%, 7/85 subjects). Most of these AEs occurred during the early stage of treatment initiation (during treatment at 20 mg). Therefore, in consideration of safety at an early stage of treatment, the starting dose in the present trial was set at 10 mg, which is lower than the starting dose of Trial 227-201-00001.

As of Oct 2019, there are no TRIs approved in Japan or overseas, and the safety profile is unknown. The 10-mg group was also included in the trial because evaluation of safety at the lower dose is beneficial when assessing the safety profile of OPC-64005.

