7.3.2 Treatment Discontinuation

After treatment assignment, a subject may stop treatment permanently for a variety of reasons. Treatment discontinuations may be initiated by a subject who is not satisfied with treatment or may become medically necessary due to AEs, required treatment with a disallowed medication or therapy, or other issues, as determined by the investigator. However, each investigator must comprehensively review the circumstances and offer the subject options for continued treatment to the degree possible as described in Section 7.3.5.

If discontinuation of IMP administration occurs during the period between the start of IMP administration after Visit 2 and the start of IMP administration after Visit 9, the examination at discontinuation will be performed. If the subject refuses to undergo any examinations at the time of withdrawal, or if examinations cannot be performed due to an emergency or other circumstances, of the examination items specified for the time of withdrawal, only those items that can be performed will be performed.

If the specified examinations have been already performed on the day of discontinuation, they do not need to be repeated.

If discontinuation occurs during the period between the start of IMP administration after Visit 2 and the start of IMP administration after Visit 3, the post-treatment observation (Visit 11) is not necessary after the examination at discontinuation has been performed.

If discontinuation is decided during the period between the start of IMP administration after Visit 4 and the start of IMP administration after Visit 9, the IMP dose will be tapered (duration: 1 week [7 days \pm 2 days]) wherever possible after the examination at discontinuation has been performed (see Section 6.1.1.4). After the dose tapering, the subject will visit the trial site to undergo the same examination as scheduled at Visit 10, and the post-treatment observation (Visit 11) will be performed 2 weeks after the date of the final dosing.

If discontinuation occurs during the period between the start of IMP administration after Visit 3 and the start of IMP administration after Visit 4, dose tapering is not necessary after the examination at discontinuation has been performed, and the post-treatment observation (Visit 11) will be performed 2 weeks after the date of the final dosing.

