5.2 Safety Analysis Set

The safety analysis set includes all subjects who were administered at least 1 dose of double-blind IMP.

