7.6 Protocol Deviations

The number and proportion of randomized subjects with major deviations from the protocol will be determined by deviation category (IMP administration, eligibility criteria, failure to discontinue the trial when the subject meets the withdrawal criteria, procedural deviation that may affect primary endpoint evaluation, prohibited concomitant medications, and overall) and trial site for overall, for each treatment group, and for the overall OPC-64005 group.

The same tabulation will be performed for all subjects who are not randomized.

8 Efficacy Analysis

The efficacy analysis will be performed on the FAS. Baseline is the last data obtained after the start of IMP administration in the placebo-lead in period and before the start of double-blind IMP administration.

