8.1.2 Sensitivity Analyses

8.1.2.1 Sensitivity Analysis for Handling of Missing Data

As a sensitivity analysis for handling of missing data, placebo multiple imputation and tipping point analysis on MNAR assumption will be performed using a pattern-mixture model with multiple imputation.

Multiple imputation analysis will be performed according to the following procedure. The number of imputations will be 100.

- 1) The Markov Chain Monte Carlo (MCMC) method will be used to impute intermittent missing data to produce a monotone missing data pattern.
- 2) The monotone regression method will be used to impute monotone missing data.
- 3) The same MMRM as that of the primary efficacy analysis will be used to analyze the multiple-imputed datasets.
- 4) The MIANALYZE procedure will be used to integrate the analysis results of the multiple-imputed datasets, and the estimate of the difference between the OPC-64005 20-mg group and the placebo group at Week 6 in the double-blind treatment period and its 95% CI and p-value will be determined.

In placebo multiple imputation, for discontinued subjects in each OPC-64005 group, MNAR will be assumed for missing data after discontinuation and an imputation model based on the placebo group will be used in imputation.

In tipping point analysis, for subjects in each OPC-64005 group who discontinued treatment for any of the following reasons, MNAR will be assumed for missing data after discontinuation.

- Withdrawal for any reason
- Withdrawal due to AEs, a lack of efficacy, or consent withdrawal
- Withdrawal due to AEs or a lack of efficacy

For subjects in each OPC-64005 group who discontinued treatment for reasons assumed as MNAR, the MAR assumption will be used to impute post-discontinuation missing data, add Δ (intergroup differences in MMRM of the primary efficacy analysis) \times k% to the imputed value, and increase k until a statistically significant conclusion is reversed ($p > 0.05$).

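### Both MNAR sensitivity analyses use a FAS that requires a post-baseline MADRS, so dosed subjects who stop before any rating are left out of the analyses meant to test informative dropout

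*SAP*

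**What the plan says.** **Analysis set.** SAP Section 8 opens with "The efficacy analysis will be performed on the FAS". SAP 5.1 (and Protocol 9.2.1) limits the FAS to dosed subjects who "have MADRS total scores at baseline and at least one time point after the start of double-blind treatment". SAP 5.2 defines a wider set with no rating condition: "The safety analysis set includes all subjects who were administered at least 1 dose of double-blind IMP".

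**MNAR analyses.** SAP 8.1.2.1 describes placebo multiple imputation and a tipping-point analysis. For the first, "for discontinued subjects in each OPC-64005 group, MNAR will be assumed for missing data after discontinuation", with imputation based on the placebo group. The second groups withdrawals by reason, and its broadest category covers withdrawal for any reason. On the model, "The same MMRM as that of the primary efficacy analysis will be used to analyze the multiple-imputed datasets". The section does not name an analysis set of its own.

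**When ratings are taken.** Protocol Table 1.3-1 schedules the first double-blind MADRS at Visit 4, Day 8 ± 1, and also marks MADRS in the discontinuation column. Protocol 1.4.7 says of a subject stopping before post-Visit 9 dosing that "the investigator will perform the examination at discontinuation specified in the schedule of assessments". Protocol 7.3.2 sets the limit. "If the subject refuses to undergo any examinations at the time of withdrawal", or if an emergency or other circumstances prevent them, only the feasible items are done.

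**Which ratings count.** SAP 3.4 assigns Days 2 to 11 to Week 1. It bars from every double-blind time point any rating taken 7 or more days after the last double-blind dose.

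**The concern.** The MNAR analyses exist because dropout may be informative. Having a post-baseline rating is a post-randomisation event, and the FAS makes it a condition of entry. The earliest dropouts with no rating are thus removed before the MNAR assumption is applied to anyone. If they fall mainly in the 20-mg arm, the sensitivity results will look more robust than the comparison of all dosed subjects would.

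The method does not force this. An MMRM on observed change scores gains nothing from a subject who has only a baseline value. Imputation by monotone regression can start from the baseline, so here only the FAS condition excludes such subjects.

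A related case has no stated rule. A subject whose only rating is barred by SAP 3.4 (for example, last dose on Day 2 and rating on Day 9, which is 9 − 2 = 7 days later) meets the literal FAS wording but has no usable post-baseline value. The SAP does not say whether or how that subject enters the imputation.

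**Working it through.** **1. The plan's own figure.** Inputs (Protocol 9.1, SAP 4): difference 4, SD 11, two-sided alpha 0.05, power 80%.

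- Normal approximation: n = 2 × (1.96 + 0.8416)² × 11² / 4² = 118.7, so 119 per group.
- Two-sample t-test: 119.7, so 120 per group, with power 80.1% at 120.

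The stated 120 per group reproduces and is not in dispute.

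**2. Standard error.** SE = 11 × √(2/120) = 1.42. The smallest significant difference is 1.96 × 1.42 = 2.78. Differences below are given as absolute values.

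**3. Placebo imputation with the omitted subjects restored.** Let x be the share of the dosed 20-mg arm with no usable rating. Imputed from the placebo model, these subjects contribute no difference from placebo on average. The all-dosed estimate is therefore FAS estimate × (1 − x). The SE is held at 1.42 and p-values are two-sided normal. The documents give no value for x, so the shares are assumptions.

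| Assumed x | FAS estimate 4.0 becomes | p | FAS estimate 2.90 becomes | p |
|---|---|---|---|---|
| 0% | 4.00 | 0.0049 | 2.90 | 0.041 |
| 2% | 3.92 | 0.0058 | 2.84 | 0.045 |
| 5% | 3.80 | 0.0075 | 2.76 | 0.052 |
| 8% | 3.68 | 0.0096 | 2.67 | 0.060 |

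**4. How borderline a result must be.** Significance is lost only if the FAS estimate lies between 2.78 and 2.78/(1 − x). At x = 5% the upper end is 2.93. If the true difference is 4, the chance of an estimate in that band is about 3%. It is about 1% at x = 2% and about 5% at x = 8%.

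**5. Tipping point, as an illustration.** Assume a MAR difference of 4, SE fixed at 1.42, 24 of 120 subjects in the 20-mg arm dropping out, and 6 of those 24 unrated. A shift of k × 4 applied to a fraction f of the arm tips the result when 4 − 4kf = 2.78, that is, k = (4 − 2.78)/(4f).

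- FAS: f = 18/114, k ≈ 193%.
- All dosed: f = 24/120, k ≈ 152%.

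Under these assumptions the FAS version reports a tipping point that looks further away than it is for all dosed subjects.

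**The case against.** **The gap is narrow.** This stands. A Week 1 stopper who attends the discontinuation examination normally gets a MADRS that falls in the Week 1 window and so enters the FAS. A reader might infer that all Week 1 dropouts are lost. The documents do not support that: only those who refuse, miss or cannot complete the rating are lost, together with those whose rating comes too late under SAP 3.4.

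**The earlier trial's dropout rates do not transfer.** This also stands. Protocol 4.3.2 reports AE discontinuation of 23.4% (18/77) against 8.5% as printed (7/85 is 8.2%), mostly early in treatment. A reader might take this as a forecast of unrated dropout here. Those patients had AD/HD and started at 20 mg, and the protocol gives that experience as its reason for starting at 10 mg in this trial. The 20-mg arm takes 10 mg in Week 1, so subjects who attend Visit 4 are rated at about the time 20 mg begins. The rates show a reason for concern and nothing more.

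**Using the primary set varies one thing at a time.** A sensitivity analysis on the FAS isolates the missing-data assumption, which is a fair argument. It is met by showing the FAS version beside the wider one.

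**Exclusion counts are already planned.** Correct. SAP 7.1 tabulates treated subjects and analysis-set membership by group, so no extra count is needed.

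**A baseline MADRS is not guaranteed.** Correct. Eligibility rests on HAM-D and MADRS-S, so the wider set still needs a baseline MADRS condition.

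**Conclusion.** The point holds in a limited form. As written, the SAP leaves dosed subjects with no post-baseline MADRS out of both MNAR analyses, although imputation could include them. The effect under placebo imputation is proportional to the share omitted: about 1% of the estimate for each 1% of the 20-mg arm. At the design difference of 4, even an assumed 8% leaves the conclusion unchanged (3.68, p = 0.0096). Only a FAS estimate just above 2.78 would lose significance.

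This rests on an unknown share, a fixed SE of 1.42, and placebo-like outcomes for the omitted subjects. A harsher assumption, such as no change from baseline, would give larger shifts, but it is not the imputation the SAP specifies and should not be used to size this point.

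A reader might also infer that the primary result is biased by the same route. The primary MMRM would give the same answer with or without baseline-only subjects, so the point concerns the sensitivity analyses alone. It is worth correcting because the change is small and the present wording weakens the analyses where they are most needed.

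**What to change.** In SAP 8.1.2.1, add:

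- Placebo multiple imputation and the tipping-point analysis are run on all randomised subjects with at least one double-blind dose and a baseline MADRS.
- For subjects with no usable post-baseline rating, including those whose only rating is excluded by SAP 3.4, all post-baseline visits are imputed, and the subject is handled under the recorded discontinuation reason.
- Both analyses are also shown on the FAS, so that the effect of the population can be separated from the effect of the missing-data assumption.

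Keep the FAS for the primary MMRM. Data collection and sample size do not change. The cost is a second input dataset for analyses already planned, a few more output tables, and possibly a slightly less favourable sensitivity estimate. Protocol Section 9 has the SAP finalised before data lock, and Protocol 9.3 leaves these details to it.
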